Study Protocol and Statistical Analysis Plan

Official Title

Development and validation of the Excessive Emotional Behaviors Scale:
long and short forms among Chinese adults with emotional distress

Short Title

Excessive Emotional Behaviors Scale Development

Document Date

23 April 2026

1. Background

Emotional disorders such as anxiety and depression represent a major contributor to the global burden of disease due to their high prevalence, recurrent course, and substantial impact on social and occupational functioning. In recent years, the transdiagnostic approach has emerged as a dominant paradigm in the study and treatment of emotional disorders. This approach is based on the assumption that different emotional disorders share common underlying psychological mechanisms.

Within this framework, emotional behaviors are conceptualized as a core mechanism involved in the onset, maintenance, and exacerbation of emotional disorders. Emotional behaviors refer to behavioral responses triggered by intense emotional experiences, typically aimed at rapidly reducing or controlling emotional distress. Although these behaviors may provide short-term relief, they often contribute to long-term maintenance of emotional problems and functional impairment.

The Unified Protocol for Transdiagnostic Treatment of Emotional Disorders identifies emotional behaviors as a key treatment target, emphasizing the reduction of avoidance and maladaptive emotional action tendencies. In parallel, within the context of Chinese clinical practice, Mindfulness Intervention for Emotional Distress has been proposed, alongside the psychopathological diamond model of emotional distress. This model suggests that emotional distress is characterized by systematic dysfunction across four domains: life engagement, distress tolerance, emotional behaviors, and cognitive flexibility. Among these, excessive emotional behaviors are considered a central hub linking emotional experiences to functional impairment.

Despite their theoretical importance, there is currently no specialized instrument designed to directly assess excessive emotional behaviors. Existing measures, such as those assessing experiential avoidance, primarily focus on internal experiences or cognitive attitudes rather than observable behavioral responses. Furthermore, many existing instruments are lengthy and contain overlapping constructs, limiting their practical utility.

Therefore, it is necessary to develop a concise, theoretically grounded, and psychometrically sound scale to assess excessive emotional behaviors.

2. Objectives and Hypotheses

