2.1 Overall Objective

The primary aim of this study is to develop and validate a self-report scale measuring excessive emotional behaviors, grounded in the Unified Protocol and Mindfulness Intervention for Emotional Distress frameworks.

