5.2 Measures

Excessive Emotional Behaviors Scale (Preliminary Version)

Developed based on qualitative phase.

Experiential Avoidance Measures

Acceptance and Action Questionnaire–II

Brief Experiential Avoidance Questionnaire

Anxiety Measure

Generalized Anxiety Disorder Scale–7

Depression Measure

Patient Health Questionnaire–9

6. Statistical Analysis Plan

This study aims to develop the Excessive Emotional Behavior Scale to assess emotional behavior patterns exhibited by individuals experiencing emotional distress. Based on the theoretical framework, the initial item pool will consist of 40 items covering four hypothesized dimensions: behavioral avoidance, cognitive avoidance, safety behavior, and emotion-driven behavior. To ensure the stability of the scale structure and the psychometric quality of the instrument, a two-stage independent-sample design will be used for scale development and validation. In the first stage, an independent sample will be recruited for item analysis and exploratory factor analysis to establish the preliminary structure of the scale. In the second stage, a new independent sample will be recruited for confirmatory factor analysis, as well as reliability and validity testing, to determine the final item composition and dimensional structure of the formal scale.

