6.1 Sample Use Strategy

A two-stage independent-sample design will be adopted in this study. In the first stage, one independent sample will be recruited for item analysis and exploratory factor analysis to preliminarily screen items and explore the latent factor structure of the scale. In the second stage, another new independent sample will be recruited for confirmatory factor analysis to test the stability and replicability of the factor structure identified in the first stage. This design helps avoid the risk of overfitting that may arise when structural exploration and structural validation are conducted within the same sample, thereby improving the rigor of structural validation and the

external stability of the findings.

The first-stage sample will be used only for item analysis and exploratory factor analysis and will not be used for confirmation of the final structural model. The second-stage sample will be used independently for confirmatory factor analysis, internal consistency testing, and the evaluation of structural validity, convergent validity, discriminant validity, and criterion-related validity. If the sample size in the second stage permits, additional competing model comparisons and supplementary model testing will also be conducted.

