6.3.5 Item Retention Criteria

The following criteria will be used for item retention during the exploratory factor analysis stage: the primary loading of an item on its intended factor should be at least 0.45; if an item has relatively high loadings on two or more factors, the difference between the primary loading and the secondary loading should be greater than 0.20 to avoid substantial cross-loading; items with very low communalities, unclear factor membership, or obvious content redundancy will also be considered for deletion. In addition to statistical criteria, the completeness of content coverage within each dimension will also be taken into account to avoid compromising construct representativeness in pursuit of statistical optimization alone.

A stepwise item reduction strategy will be used. After each deletion, exploratory factor analysis will be rerun until a candidate version of the scale with a clear structure, well-defined item-factor relationships, satisfactory statistical indicators, and sound theoretical interpretability is obtained. At the end of the first stage, a preliminary structural model and a candidate set of items for the Excessive Emotional Behavior Scale will be established.

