6.6 Principles for Final Item Selection

The final number of items in the formal scale will not be fixed in advance but will be determined after completion of item analysis, exploratory factor analysis, confirmatory factor analysis, and reliability and validity testing. Final item retention will follow the following principles: first, items should show satisfactory statistical performance, including adequate factor loadings, reasonable communalities, and a positive contribution to internal consistency; second, item content should accurately reflect the core meaning of the intended dimension; third, each dimension should retain a sufficient number of items to ensure structural stability and content representativeness. In principle, each dimension should retain no fewer than three items to ensure the basic stability of latent variable measurement.

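### The title promises validated long and short forms, but the plan develops and tests one scale and gives no objective, selection rule, timing or analysis for a short form

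*Combined protocol and SAP*

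**What the plan says.** The official title covers development and validation of the Excessive Emotional Behaviors Scale in "long and short forms among Chinese adults with emotional distress". That is the only mention of a short form in the document; the Short Title entry beneath it is just the study's abbreviated name.

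The rest of the plan speaks of one instrument:

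- **Section 1 (Background)** concludes that "it is necessary to develop a concise, theoretically grounded, and psychometrically sound scale".
- **Section 2.1** sets the aim to "develop and validate a self-report scale measuring excessive emotional behaviors". The specific objectives and hypotheses in 2.2 and 2.3 do not mention a second form.
- **Section 6, opening paragraph:** "the initial item pool will consist of 40 items covering four hypothesized dimensions".
- **Section 6.1:** "A two-stage independent-sample design will be adopted in this study", and "The first-stage sample will be used only for item analysis and exploratory factor analysis". The second sample is for confirmatory factor analysis (CFA), reliability and validity.
- **Section 6.3.5** ends Stage 1 by saying that "a preliminary structural model and a candidate set of items for the Excessive Emotional Behavior Scale will be established".
- **Section 6.6:** "The final number of items in the formal scale will not be fixed in advance". The number is settled once item analysis, both factor analyses and the reliability and validity tests are complete.
- **Section 6.8** lists reliability and validity results for a single total scale and its dimensions.

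**The concern.** A short form is a separate instrument. It needs its own item-selection rule and its own evidence of structure, reliability and validity, preferably from people whose answers did not shape the selection. The plan provides none of these, so one of the two products in the title would have no planned evidence behind it.

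Timing adds to the problem. Section 6.1 justifies two samples on the ground that exploring and validating a structure in one sample risks overfitting. Yet the opening of Section 6, Section 6.5.1 and Section 6.6 let Stage 2 results shape the final items. Anyone who shortened the scale once it was final would have no unused data to test the result on.

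**Working it through.** The main point is an omission, so it is checked by reading. The arithmetic that follows shows why the omission matters.

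**1. Elements a validated short form needs, set against the plan**

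| Element | In the plan? |
|---|---|
| Objective or hypothesis | No (2.1 to 2.3: one scale) |
| Target length | No (6.6 leaves the length of the one scale open; its minimum of three items per dimension is a floor for that scale) |
| Selection rule and time of selection | No (6.3.5 produces one candidate set) |
| CFA, reliability, validity | No (6.4 and 6.5: one scale) |
| Reporting | No (6.8: one total scale and its dimensions) |

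**2. Is there room for a third sample?** Section 5.1 gives 5 to 10 participants per item and a total of 550. With 40 items:

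- One sample: 5 × 40 = 200 to 10 × 40 = 400.
- Two samples: 400 to 800.
- 550/40 = 13.75 per item as a single sample, which is above the rule. Split evenly (an assumption, since no split is given), 275/40 = 6.9 per item per stage.

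The rule does not yield 550 as a unique figure, but 550 fits as a two-sample total. Arithmetic alone does not exclude a third sample, because two samples at the minimum ratio would leave 550 − 400 = 150. The text is what settles it: Section 6.1 describes two samples, assigns each its uses, and gives neither a short-form task.

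**3. Can long-form reliability stand in for the short form?** Section 6.5.1 takes alpha and omega of at least 0.70 as acceptable. For k items with equal standardized loading λ, omega = (kλ)² / [(kλ)² + k(1 − λ²)]. Taking λ = 0.60 as an assumption (the retention floor in 6.3.5 is 0.45):

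- Six items: 12.96 / (12.96 + 3.84) = 12.96/16.80 = 0.77, a pass.
- Five items: 9.00 / (9.00 + 3.20) = 9.00/12.20 = 0.74, a pass.
- Four items: 5.76 / (5.76 + 2.56) = 5.76/8.32 = 0.69, just short.
- Three items: 3.24 / (3.24 + 1.92) = 3.24/5.16 = 0.63, a fail.

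For three items to reach 0.70, 3λ²/(1 − λ²) must be at least 0.70/0.30 = 2.33, so λ² = 0.4375 and λ is about 0.66. A dimension could therefore pass in the long form and fail in the short form, and no planned analysis would show it.

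**4. Selecting and testing on the same data (illustration).** The inputs here are assumptions, not taken from the documents: one dimension of 8 items, loadings averaging 0.60 with SD 0 or 0.05, the best 3 chosen by inter-item correlation, 1,500 runs per setting.

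| n | Loading SD | Mean alpha, selection sample | Mean alpha, new sample | Chance of alpha ≥ 0.70, selection vs new |
|---|---|---|---|---|
| 275 | 0 | 0.684 | 0.626 | 26% vs 2% |
| 275 | 0.05 | 0.703 | 0.663 | 54% vs 22% |
| 550 | 0 | 0.668 | 0.628 | 4% vs 0.1% |
| 550 | 0.05 | 0.693 | 0.670 | 42% vs 23% |

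The overstatement in mean alpha is 0.04 to 0.06 at n = 275 and 0.02 to 0.04 at n = 550. It is small in absolute terms, but near the 0.70 line it can change the conclusion.

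**The case against.** **The title may simply be loose.** Sections 1 and 2.1 aim at one concise scale, so the reference to short forms could be a stray phrase that a title edit would cure. That is a fair possibility, and the fix allows for it. Until the edit is made, the title claims something the plan does not do.

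**The 40-item pool could be the long form and the reduced scale the short form.** The documents never say so. Section 6.3.1 screens the 40 items, 6.3.2 carries forward only those retained, and no validation of the 40-item version is planned. On this reading the long form is the unvalidated one, and the title is still not met.

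**The plan does not say that a short form would be taken from Stage 2 results.** This stands. A reader might infer that a short form could only be picked after Stage 2, or that the design cannot deliver one. The documents do not support either inference. They are silent on when a short form would be chosen, and nothing prevents fixing a subset from Stage 1 data. The same-data problem applies to a form cut from the final scale.

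**The plan guards against overfitting.** Section 6.4.5 limits changes driven by modification indices, and 6.5.1 and 6.6 weigh content and theory as well as statistics. These safeguards reduce selection bias in the formal scale but supply no test of a shorter one.

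**Conclusion.** The point holds as a contradiction between the title and the plan. The study as written develops, tests and reports one scale and validates no short form. That conclusion rests on reading alone and needs no simulation.

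The conditional part also holds: because final items are fixed only after Stage 2 data have been used, and no further sample is described, a short form cut from the final scale would be selected and tested on the same people.

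The sizes are illustrative. Under equal loadings of 0.60, omega falls from 0.77 with six items to 0.63 with three. Same-sample selection overstates mean alpha by about 0.02 to 0.06 under the assumed loadings, item counts and sample sizes. A reader might also treat an inflated correlation between long and short forms as part of the defect. The plan proposes no such correlation, so it is not counted here.

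The change should be made, and before Stage 2 data are seen, because the two-sample design can supply the independent test only if the short form is fixed by then.

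**What to change.** Choose one of two routes.

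**Keep the short form.**

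- Add it to Section 2 as an objective.
- At the end of 6.3.5, select its items from Stage 1 data by a stated rule that weighs loading, redundancy and content coverage. Loading alone could narrow the content, which 6.3.5 itself cautions against.
- Set the number of items per dimension so that the Stage 1 loadings project to omega of at least 0.70. The minimum of three in 6.6 should not be taken as the target by default. Leave a margin, since loadings of items chosen in the same sample tend to be optimistic.
- Freeze the list before any Stage 2 data are seen.
- In Stage 2, run separately for the short form: CFA, omega, discriminant validity, and correlations with the GAD-7, PHQ-9, AAQ-II and Brief Experiential Avoidance Questionnaire. Add these to 6.8.
- State in 6.6 that any frozen short-form item later dropped from the long form will be reported, and that a short form altered for this reason will be labelled as not independently validated.

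**Or drop it.** Remove the short form from the title and from any claims.

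**Cost.** The first route needs additional wording and a repeat of the Stage 2 analyses on an item subset, with no extra participants. One limitation remains to be reported: short-form answers would still come from people who completed the full form. The second route costs only a title edit.

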2.1 Overall Objective

The primary aim of this study is to develop and validate a self-report scale measuring excessive emotional behaviors, grounded in the Unified Protocol and Mindfulness Intervention for Emotional Distress frameworks.

2.2 Specific Objectives

To define the construct and dimensions of excessive emotional behaviors.

To identify real-world behavioral patterns through qualitative methods.

To examine the factor structure, reliability, and validity of the scale.

To explore associations between excessive emotional behaviors and emotional symptoms.

2.3 Hypotheses

Excessive emotional behaviors represent a multidimensional construct, including:

behavioral avoidance

cognitive avoidance

safety behaviors

emotion-driven actions

The scale will demonstrate good internal consistency and structural validity.

Scale scores will be positively associated with anxiety and depressive symptoms.

Excessive emotional behaviors will be related to, but distinguishable from, experiential avoidance.

3. Study Design

This study adopts a mixed-methods design consisting of:

Study 1: Qualitative study (cognitive interviews)

Study 2: Quantitative study (scale development and validation)

4. Study 1: Qualitative Phase

4.1 Objective

To evaluate item clarity, relevance, and ecological validity through cognitive interviews.

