4.2 Participants

Approximately 18 participants with anxiety or depressive distress will be recruited.

Inclusion Criteria

Age ≥ 18 years

Experience of emotional distress

Ability to understand and communicate in Chinese

Provision of informed consent

Exclusion Criteria

Acute psychosis or severe psychiatric disorders

Cognitive impairment

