4.3 Procedure

Semi-structured interviews (~50 minutes) will include:

Rapport building

Cognitive interviewing (think-aloud + probing)

Structural evaluation

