4.4 Data Analysis

Thematic analysis will be conducted:

Open coding

Theme development

Mapping to item pool

Two independent coders will analyze data.

5. Study 2: Quantitative Phase

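### The objective of identifying real-world behaviours has no elicitation step in Study 1, and no stated route by which a new theme becomes an item

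*Combined protocol and SAP*

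**What the plan says.** Five places in the combined protocol and SAP bear on this.

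- **Objective.** Section 2.2 sets out "To identify real-world behavioral patterns through qualitative methods".
- **Study 1 purpose.** Section 3 describes Study 1 as a cognitive interview study, and Section 4.1 gives its aim as "To evaluate item clarity, relevance, and ecological validity through cognitive interviews". Section 4.2 sets the size: "Approximately 18 participants with anxiety or depressive distress will be recruited".
- **Study 1 content and analysis.** Section 4.3 outlines semi-structured interviews of about 50 minutes with three parts: rapport building, think-aloud with probing, and structural evaluation. Section 4.4 lists open coding, theme development and, last, "Mapping to item pool", with two independent coders.
- **Origin of the items.** Section 5.2 says of the preliminary scale "Developed based on qualitative phase". The opening of Section 6 says "Based on the theoretical framework, the initial item pool will consist of 40 items covering four hypothesized dimensions".
- **What Study 2 does with items.** Section 6.3.1 takes the 40 items into item analysis and considers them for deletion. Section 6.3.5 reduces them stepwise. Section 6.6 sets principles for retention.

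**The concern.** Evaluating items and identifying behaviours are different tasks. Cognitive interviewing shows whether people understand the items in front of them and find them relevant. It is not designed to find out what people do that no item mentions. For that they must be asked openly, and asked before the items suggest the answers. The plan gives a procedure only for the first task.

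What is at stake is content coverage. Section 1 justifies the new scale by saying that existing measures look at inner experience more than at observable behaviour. Section 8 claims better ecological validity from combining qualitative and quantitative work. If a common behaviour is missing from the pool, those claims rest on reactions to the items supplied. Factor analysis of the supplied items cannot show that something is absent.

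**Working it through.** The plan gives no figure to reproduce on this point. The main check is a comparison of sections. The arithmetic that follows is only illustrative.

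**Step 1. Objective against procedure.** Section 2.2 asks for behavioural patterns to be identified. Section 4.1 asks for items to be evaluated. None of the three parts in Section 4.3 is an open question about behaviour placed before the items, so the Section 2.2 objective has no specified procedure.

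**Step 2. From theme to item.** Section 4.4 codes openly, develops themes and maps them to the pool. Mapping presupposes that a pool exists. A theme either matches an item or does not, and the second case has no stated consequence.

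**Step 3. Two origins.** Section 5.2 derives the preliminary scale from the interviews. Section 6 derives a pool of stated size and dimensions from theory. Both can be true if theory supplies a draft that Study 1 revises, but no section says so or says when the 40 items become final.

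**Step 4. Can Study 2 recover a missing behaviour?** Sections 6.3.1, 6.3.5 and 6.6 delete or retain. Section 6.3.4 lets the number of factors depart from theory, but only among items already administered. Section 6.4.5 allows limited model modification and no new items. Whatever is absent when Study 2 starts stays untested.

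**Step 5. Is 18 interviews the limit?** Assume that a share p of distressed adults show a behaviour and that each would report it if asked openly. The chance of at least one mention in n = 18 (Section 4.2) is 1 − (1 − p)^18:

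- p = 5%: 1 − 0.95^18 = 0.603
- p = 10%: 1 − 0.90^18 = 0.850
- p = 15%: 1 − 0.85^18 = 0.946
- p = 20%: 1 − 0.80^18 = 0.982

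The prevalences are assumptions; the documents give none. On them, the planned number of interviews is enough to bring up common behaviours. What is missing is the question. Requiring two mentions before a theme counts would lower the yield: at p = 15%, 1 − 0.85^18 − 18 × 0.15 × 0.85^17 = 0.78.

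**Step 6. Time.** An open block of 10 minutes leaves 50 − 10 = 40 minutes for everything else. If each participant saw all 40 items, which the documents do not state, that is at most 40/40 = 1 minute per item, before time for rapport and structural evaluation is taken off. With a rotated half of the items each, it is at most 40/20 = 2 minutes, and 18/2 = 9 people probe each item. For a comprehension problem affecting an assumed 25% of people, the chance that at least one prober meets it goes from 1 − 0.75^18 = 0.99 to 1 − 0.75^9 = 0.92. For an assumed 10%, it goes from 0.85 to 1 − 0.90^9 = 0.61.

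**The case against.** The strongest reply is that the plan is more open than it looks. Section 4.3 is a short outline and not the full interview guide. The interviews are semi-structured and include probing, and open coding and theme development come before any mapping. Section 5.2 says that the scale is built on the qualitative phase, which leaves room to revise the items before Study 2. Theory-led item writing followed by cognitive interviews is also a coherent design that matches the label in Section 3.

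Much of this stands, and it rules out a stronger reading. A reader might infer that Study 1 merely debriefs people on a pool already closed at 40 items and four dimensions, so that other behaviours cannot surface and the objective cannot be met. The documents do not support that. Inductive steps are listed. The date at which the 40 items are fixed is not given. The four dimensions are hypotheses, from which Section 6.3.4 allows the exploratory analysis to depart.

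What the reply does not supply is a procedure. Behaviours that come up by chance during item probing come from people who have already seen the items, and no rule says what is done with them.

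A second reply is that rewording the Section 2.2 objective would remove the mismatch without touching the interviews. That would make the objective consistent with Section 4.1. Section 5.2 would still conflict with Section 6, and unmatched themes would still have no route into the pool.

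**Conclusion.** The point holds in this form: the objective of identifying real-world behaviours has no specified elicitation step, the plan does not say how a theme outside the pool changes the items, and it gives two unreconciled origins for the scale. A behaviour not added before Study 2 cannot be tested there.

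The effect is on content coverage and on the ecological-validity claim. It cannot be put as a number from the documents. The detection probabilities rest on assumed prevalences and on full reporting, and serve only to show that the 18 interviews need not be increased. That some pool exists at interview is implied by Sections 4.1 and 4.4; that it is final by then is not stated.

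The change should be made before interviewing starts, because a participant who has seen the items can no longer answer unprompted.

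**What to change.** 1. **Section 4.3:** place an open block of about 10 minutes, on recent episodes of distress and what the person did, before any item is shown.
2. **Section 4.4:** code these answers before mapping them to the pool, and review every theme that maps to no item as a candidate item, recording the decision and the reason.
3. **Section 5.2 and Section 6:** reconcile the two origins by calling the 40 items a provisional, theory-based pool that Study 1 may revise and that is fixed when Study 1 ends. Section 6.3.1 should then refer to the fixed pool.

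**Cost:** changes to the interview guide and protocol wording, with no extra participants or visits. About 10 of the 50 minutes is lost to item probing. If time is short, each participant can be given a rotated half of the items, so that about 9 of the 18 people probe each item, with the loss shown in Step 6. The pool may end slightly above or below 40, and the participants-per-item figure in Section 5.1 should then be read against the final count.
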